5.2 Primary Endpoint

1a) 20/20% consistency evaluation with the reference value which is expressed by the agreement rate.
 Sensor values from primary sensor will be compared to YSI™* plasma glucose values during YSI
 FSTs to analyze the agreement rate. Consistency rate = A + B:

A = (the number of pairs of the relative deviation of sensor value from primary sensor minus YSI^{m*} value is within $\pm 20\%$ /total number of pairs) * 100% (when the blood glucose concentration is greater than 4.4 mmol/L (80 mg/dL), percentage of results with relative deviations from the reference value within $\pm 20\%$);

B = the number of pairs of the deviation of sensor value from primary sensor minus YSI^{TM*} value is within \pm 20 mg/dL /total number of pairs) * 100% (when the blood glucose concentration is less than or equal to 4.4 mmol/L (80 mg / dL), percentage of results with deviations from the reference value within \pm 1.1 mmol/L (20mg/dL).

1b) Sensor values from primary sensor will be compared to YSI^{TM*} plasma glucose values during YSI^{TM*} FSTs. A mean rate in Zone A+B of Consensus Error Grid between Guardian Sensor (3) values and YSI^{TM*} plasma glucose values during YSI^{TM*} FST days

- 1c) Sensor values from primary sensor will be compared to YSI™* plasma glucose values during YSI™* FSTs. A mean rate in Zone A+B of Clarke Error Grid between Guardian Sensor (3) values and YSI™* plasma glucose values during YSI™* FST days
- 1d) Sensor values from primary sensor will be compared to YSI^{TM*} plasma glucose values during YSI^{TM*} FSTs. A mean absolute relative difference (MARD) between Guardian Sensor (3) values and YSI^{TM*} plasma glucose values during YSI^{TM*} FST days

The MARD is calculated by the following formula:

$$ARD_{k} = 100\% \frac{\left| y_{CGM}(t_{k}) - y_{ref}(t_{k}) \right|}{y_{ref}(t_{k})}$$

$$MARD = \frac{1}{N} \sum_{k=1}^{N} ARD_{k}$$

5.3 Inclusion and Exclusion Criteria

Inclusion Criteria:

- Subject is 14 75 years of age at time of screening
- Subject has a clinical diagnosis of type 1 or 2 diabetes as determined via medical record or source documentation by an individual qualified to make a medical diagnosis
- Subject has adequate venous access as assessed by investigator or appropriate staff
- Subject is willing to follow the study procedures and willing to come to study visits.

Exclusion Criteria:

- 1. Subject will not tolerate tape adhesive in the area of Guardian™ Sensor (3) placement as assessed by qualified individual.
- 2. Subject has any unresolved adverse skin condition in the area of study device or device placement (e.g., psoriasis, rash, Staphylococcus infection)
- 3. Subject is actively participating in an investigational study (drug or device) wherein they have received treatment from an investigational study (drug or device) in the last 2 weeks
- 4. Subject is female and has a positive pregnancy screening test
- 5. Females of child bearing age and who are sexually active should be excluded if they are not using a

form of contraception deemed reliable by investigator

- 6. Subject is female and plans to become pregnant during the course of the study
- 7. Subject has a hematocrit (Hct) lower than the normal reference range
- 8. Subject may not be on the research staff of those performing this study

5.4 Study Timeline

The subject's participation from study start to completion is approximately 1-3 weeks (including replacement sensor wear and repeat in-clinic procedures).

Additional rescheduled visits could occur if Guardian™ Sensor (3)s dislodge and new Guardian™ Sensor (3)s must be re-inserted (See Replacement Sensors, Section 9.6)

- Visit 1: Consent and Screening
- Visit 2: Random Assignment
 - Visit 1 and 2 can be combined, however all eligibility criteria on Visit 1 should be met, including review of Hct prior to Visit 2.
 - O Visit 1 and Visit 2 should be no more than 2 weeks apart.
- Visit 3: Study & Device Training
 - o Two Guardian™ Sensor (3)s each connected to a Guardian™ Connect transmitter
 - Dispense Patient Log Sheet if CONTOUR^{TM*} study meter BG software and cable is not accessible at time of the study start
- Visit 4: YSITM* FST
 - Study and device training (Day 1 subjects who have not already received study and device training from Visit 3)
 - O Subjects will undergo one YSITM* FST on any one of the following sensor wear days:
 - Day 1
 - Day 3 5
 - Day 7
- Visit 5: End of Study (EOS) Visit
 - GuardianTM Connect transmitters removed (Please note that the subject should target

wearing the device for 170 hours or longer from time of insertion)

- o Investigational center staff will:
 - Download the Guardian™ Connect transmitters data from GST Download
 Utility Software following completion of the study devices wear
 - Download subject's CONTOUR^{TM*} study meter BG values
 - Collect subject's Patient Log Sheet if CONTOUR^{TM*} study meter BG software and cable is not accessible at time of the study start
 - Provide CONTOUR^{TM*} study meter and GuardianTM Connect transmitter data to sponsor
- Return study devices
- Subject complete questionnaires

6. General Statistical Considerations

6.1 Study Hypothesis

Statistical testing

At 1a), 1b), and 1c) evaluation criteria, one proportion Z test will be used for the analysis of the primary endpoint. The 97.5% lower confidence limit of the agreement rate, the mean rate in Zone A+B of Consensus Error Grid, and the mean rate in Zone A+B of Clarke Error Grid will be tested against corresponding threshold, respectively.

At 1d) evaluation criteria, one sample T test will be used and the 97.5% upper confidence limit of the MARD will be tested against corresponding threshold.

The study will be considered as a success only when the four evaluation criteria (1a), 1b), 1c), and 1d)) meet the pre-defined thresholds.

6.2 Sample Size Determination

The sample size selected is based on the primary effectiveness endpoints, which are 1a) a within 20% agreement rate, 1b) a mean rate in Zone A+B of Consensus Error Grid, 1c) a mean rate in Zone A+B of Clarke Error Grid, and 1d) a MARD.

The primary endpoints of 1a) a within 20% agreement rate, 1b) a mean rate in Zone A+B of Consensus Error Grid, and 1c) a mean rate in Zone A+B of Clarke Error Grid are event rates, the estimated formula for sample size is as below:

$$n = \frac{\left[\mu_{1-\alpha}\sqrt{p_0(1-p_0)} + \mu_{1-\beta}\sqrt{p_T(1-p_T)}\right]^2}{(p_T - p_0)^2}$$

 p_T is the efficacy level of the test group, p_0 is the target value level, μ indicates the quantile to which the standard normal distribution corresponds. When α level is 0.025 (one sided), $\mu_{l-\alpha}$ is 1.96; when β is 0.2, $\mu_{l-\beta}$ is 0.845.

Based on previous studies, assuming that for 1a) a within 20% agreement rate p_T is 0.65, p_0 is 0.6, 1,200 measuring points will provide power greater than 80% to demonstrate that 1a) is great than 0.6. Assuming each subject provides the results of at least 20 measuring points during YSI FST, including 60 subjects will meet sample size requirements. Considering 20% drop out, 72 subjects need to be enrolled.

Based on previous studies, assuming that for 1b) a mean rate in Zone A+B of Consensus Error Grid or 1c) a mean rate in Zone A+B of Clarke Error Grid P_T is 0.95, P_0 is 0.9, 1,200 measuring points will provide power greater than 80% to demonstrate that 1b) or 1c) is great than 0.9. Assuming each subject provides the results of at least 20 measuring points during YSI FST, including 60 subjects will meet sample size requirements. Considering 20% drop out, 72 subjects need to be enrolled.

The primary endpoint of 1d) a MARD is a continuous variable, the estimated formula for sample size is as below:

$$n = \frac{(\mu_{1-\alpha} + \mu_{1-\beta})^2 \sigma^2}{(x_T - x_0)^2}$$

 x_T is the MARD of the test group, x_0 is the MARD target value level, μ indicates the quantile to which the standard normal distribution corresponds. When α level is 0.025 (one sided), $\mu_{1-\alpha}$ is 1.96; when β is 0.2, $\mu_{1-\beta}$ is 0.845.

Bases on previous studies, assuming that for 1d) a MARD x_T is 18, x_0 is 20, σ is 5, 60 subjects will provide power greater than or equal to 80% to demonstrate that MARD value at subject level is less than 20%. Considering 20% drop out, 72 subjects need to be enrolled.

In conclusion, to meet the sample size requirements of four 1a), 1b), 1c), and 1d), it is determined that a total of 72 subjects are included.

6.3 Analysis Population

Full analysis set (FAS#1): a set of subjects who have at least one Guardian Sensor inserted.

Full analysis set (FAS^{#2}): a set of subjects who have at least one Guardian Sensor inserted and have at least one paired Guardian Sensor and YSI^{TM*} measurement.

Per-Protocol Set (PPS) refer to the subgroup population of FAS^{#2} who have no major protocol deviations (subjects that violate the inclusion criteria, meet the exclusion criteria, etc.).

Safety Set (SS) refer to all enrolled subjects.

Primary efficacy analysis will be analyzed based on both the FAS^{#2} and PPS. All the baseline demographic data will be analyzed based on the FAS^{#1}. Safety evaluation will be analyzed based on SS.

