8.2. Subject Enrollment

Subjects will be considered enrolled in the study upon signing the Informed Consent Form (ICF).

A subject will be assigned a unique study subject identification (SID) via the eCRF during Visit 1.

The investigator will maintain a log of all subjects enrolled in the clinical study, assigning a SID linked to their names, alternative SID or contact information.

CIP320 Clinical Investigation Plan 10768467DOC Version C Page 35 of 97 Medtronic

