9.2.2. Visit 1: Consent and Screening

Overview General

Investigational center staff will:

- Obtain ICF from the subjects
- Assess subject eligibility to participate in the study
- Obtain demographic and baseline characteristics including:
 - Age
 - Gender
 - o Race
 - Ethnicity
 - Height and Weight

Note: Body Mass Index (BMI) will be calculated automatically in the study database, based on height and weight measurements entered.

- Concomitant medications (Screening Only)
- Type of diabetes
- Date of diabetes diagnosis
- Complete required screening tests, if all eligibility criteria are met:
 - o Perform urine test for pregnancy, female subjects of child bearing age or capability
 - Obtain blood sample for Hct
 - Send to local laboratory for required screening tests. (There is no point of care (POC) testing for Hct).
 - Subjects may not participate in the study training without Hct; Hct value must be reviewed for exclusion criteria prior to Visit 2
 - Note: For out of range Hct lab result, a single re-test is permitted
- Obtain blood sample and send to local laboratory for A1C (not an eligibility criteria)
- Enter eCRFs into the study database as appropriate
- Schedule next visit date and time

The study is open to all individuals who meet the eligibility criteria of the study. The investigational center will be responsible for determining adequate source documents to verify subject eligibility. Subjects who do not meet the eligibility requirements for participation in the study will be entered into the database as screen failures. Applicable eCRF(s) will be completed for all subjects who signed an ICF, whether they are eligible or ineligible to participate. If a subject fails screening criteria (e.g. Hct or pregnancy test) they will be notified regarding their

CIP320 Clinical Investigation Plan 10768467DOC Version C Page 40 of 97 Medtronic

ineligibility immediately, either in person or via telephone). Eligible subjects will return to the investigational center to be randomly assigned and begin study training at Visit 2.

Visit 2 may be completed on the same day as Visit 1, provided that Hct and pregnancy test results are available and all other eligibility criteria are met.

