14.6. Analysis Populations, Handling of Missing Data, Error

Data entry error or non-reasonable values will be cleaned before data analysis. No imputations will be done for missing data.

The Intention to Treat (ITT) Population is defined as all enrolled subjects who have at least one $Guardian^{TM}$ Sensor (3) inserted.

The Per Protocol (PP) Population is defined as subjects who completed the study, with no major deviations.

Efficacy Population is defined as the same as the ITT Population.

Safety Population is defined as all enrolled subjects.

10768467DOC Version C

Page 75 of 97

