6.4 Analysis Population Set Determination Details

- (1) No Guardian Sensor inserted: Subjects obtain randomly assigned FST, but have no Guardian Sensor inserted.
- (2) No paired Guardian Sensor and YSI TM* measurement: Subjects obtain randomly assigned FST and have a Guardian Sensor inserted, but have no paired Guardian Sensor and YSI measurement.
- (3) Violation of Inclusion/Exclusion criteria: Subjects do not meet the inclusion criteria or meet the exclusion criteria pre-specified in the protocol, and this protocol deviation may severely affect the results of primary effective endpoint. Whether protocol deviation severely affect the results of primary effective endpoints will be judged together by sponsor, investigators and statistician through discussion;
 - (4) SS= Number of subjects enrolled;

FAS#1= Number of the subjects randomly assigned FST- Number of subjects who have no Guardian Sensor inserted;

FAS^{#2}= Number of FAS^{#1} - Number of subjects who have no paired Guardian Sensor and YSI ^{TM*} measurement;

PPS= Number of FAS^{#2} - Number of subjects who have major protocol deviations (i.e. violate inclusion and exclusion criteria, etc.).

The listing of subjects who have no Guardian Sensor inserted or have major protocol deviations will be listed, including the center number, subject ID, randomly assigned FST, gender, age, type, details, FAS^{#1}, FAS^{#2} and PPS.

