7.1 Subject Disposition

The number of subjects enrolled in the study will be presented. The reasons for discontinuing prior to study completion will be summarized.

Version: V1.0

(1) Subjects Enrolled: Subjects who were enrolled in study.

- (2) Screening Failure: The subject did not meet eligibility criteria on visit 1 and did not enter visit 2: random assignment. (Does the subject meet all inclusion criteria, no exclusion criteria, and randomization conditions collected in CRF was "No").
- (3) Subjects Randomly Assigned FST: The subject entered visit 2: random assignment. (Does the subject meet all inclusion criteria, no exclusion criteria, and randomization conditions collected in CRF was "Yes").
- (4) Subjects entering FST: The subject inserted Guardian Sensor successfully and entered visit 4: FST with YSI^{TM*}. (This item is determined based on the subjects' YSI^{TM*} information).
- (5) Subjects completing the Study: Subjects completing Study: The subject completed the last visit. (This item is determined by the section study exit collected in CRF).
- (6) Subjects discontinuing from the study: The subject did not complete the last visit. (This item is determined by the section study exit collected in CRF).

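### The Safety Set counts everyone who signs consent, so subjects who never had a sensor sit in the denominator of per-subject device-related AE, SADE and UADE rates

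*SAP*

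**What the plan says.** - **When enrolment occurs.** Protocol 8.2: "Subjects will be considered enrolled in the study upon signing the Informed Consent Form (ICF". The haematocrit sample and urine pregnancy test follow at Visit 1 (Protocol 9.2.2).
- **What happens to ineligible subjects.** Protocol 9.2.2: "Subjects who do not meet the eligibility requirements for participation in the study will be entered into the database as screen failures". SAP 7.1 describes a screening failure this way: "The subject did not meet eligibility criteria on visit 1 and did not enter visit 2: random assignment". Sensors are inserted at Visit 3, or at Visit 4 for some Day 1 subjects, so a screening failure never receives one.
- **Who is in the safety set.** SAP 6.3: "Safety Set (SS) refer to all enrolled subjects". Protocol 14.6: "Safety Population is defined as all enrolled subjects". SAP 6.4 gives the count with nothing subtracted: "SS= Number of subjects enrolled".
- **What the set is used for.** SAP 6.3: "Safety evaluation will be analyzed based on SS". SAP 7.9 lists device-related AE, procedure-related AE, SADE and UADE among the events to be summarised and names no other denominator.
- **The exposed group.** SAP 6.3 defines FAS#1 as "a set of subjects who have at least one Guardian Sensor inserted". It is assigned to the baseline tables and is the starting point for FAS#2, but it is not used for safety.

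**The concern.** A person excluded at Visit 1 for low haematocrit cannot have a sensor-site infection, a SADE or a UADE. The same is true of a subject who is randomly assigned but leaves before insertion. Each such subject adds one to the denominator of a per-subject device rate and can add nothing to the numerator, so the bias runs one way, towards a safer-looking device.

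This matters because Protocol 4.2 makes the safety of the sensor part of the primary purpose, and the descriptive AE summaries are the main safety evidence the trial will give. There is also a mismatch between tables: baseline characteristics are reported on FAS#1 and safety on a larger set, so the two will have different Ns whenever anyone is unexposed.

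**Working it through.** **Step 1: does enrolled mean consented throughout?** Protocol 8.2 defines enrolment by consent. SAP 7.1 has separate items for subjects enrolled, screening failures and subjects randomly assigned. SAP 6.4 starts the FAS#1 count from those randomly assigned but the SS count from those enrolled. The SAP therefore treats these as two groups, and no passage in either document redefines enrolment.

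**Step 2: the planned size.** Protocol 14.5 and SAP 6.2 take 60 subjects and allow 20% for drop out: 60 × 1.20 = 72. This reproduces the stated figure. Under the consent definition, 72 is also the largest planned Safety Set.

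**Step 3: the dilution.** Let u be the number of the 72 who never have a sensor, and e the number of subjects with a device-related event.

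- Rate on exposed subjects = e / (72 − u)
- Rate on the Safety Set = e / 72
- Ratio of the second to the first = (72 − u) / 72
- Relative understatement = u / 72

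The documents give no value for u. The range 0 to 12 is an assumption: its upper end treats the whole gap between 72 enrolled and 60 completers as unexposed. The event counts of 3 and 6 are illustrative.

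| u | Exposed | Ratio | Relative understatement | e = 3: exposed vs SS | e = 6: exposed vs SS |
|---|---|---|---|---|---|
| 0 | 72 | 1.000 | 0% | 4.17% vs 4.17% | 8.33% vs 8.33% |
| 4 | 68 | 0.944 | 5.6% | 4.41% vs 4.17% | 8.82% vs 8.33% |
| 7 | 65 | 0.903 | 9.7% | 4.62% vs 4.17% | 9.23% vs 8.33% |
| 12 | 60 | 0.833 | 16.7% | 5.00% vs 4.17% | 10.0% vs 8.33% |

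The ratio does not depend on e, and it is below 1 whenever u is at least 1.

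**Step 4: which safety outputs are affected?**

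- *Device-related AE, SADE, UADE per subject:* diluted, because exposure to the device is a precondition for the event.
- *Procedure-related AE overall:* not diluted by screen failures as such. Protocol 11.2 counts laboratory draws as study procedures, and Protocol 9.2.2 has blood taken at Visit 1.
- *FST-specific procedure AE:* diluted, because only subjects who reach FST are at risk.
- *Skin assessment per site:* not diluted. Protocol 11.7 calls for an assessment at every sensor removal, so a subject with no sensor contributes no site. A skin finding that qualifies as an AE and is judged device-related falls under the first item.

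**The case against.** The best defence is that the definition has a purpose. Protocol 11.2 requires AEs to be recorded for as long as a subject is enrolled, and a consent-based set ensures that none is lost. That is a good reason to list AEs on all enrolled subjects. It is not a reason to use the same set as the denominator for events that need a sensor.

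Other objections stand in part:

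- SAP 7.9 promises only descriptive summaries. It does not spell out per-subject percentages, and the table shells are in an appendix that is not part of the text. The dilution is inferred from SS being the only safety denominator stated.
- The size is unknown and may be zero. SAP 6.2 labels the allowance above 60 as drop out, and anyone lost after insertion was exposed.
- No decision rests on these rates. Success depends on the four accuracy criteria (Protocol 14.9), and the UADE stopping rule (Protocol 9.14) needs no denominator.
- The disposition counts and the listing in SAP 6.4 would let a careful reader recompute the rates on exposed subjects. The reported figure would still be the diluted one.

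A reader might go further and infer that every safety rate is diluted, including procedure-related AEs and skin results. Step 4 shows that the documents do not support that. A reader might also infer that the upper confidence bound for a zero-event outcome will be too low. Neither document plans such a bound, so this is not a fault in a planned output.

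**Conclusion.** The point holds for per-subject device-related AE, SADE and UADE rates, and for FST-specific procedure AEs. The definitions in the two documents agree with each other, and together they place never-exposed subjects in the denominator.

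For the device rates, the understatement is 0 to 16.7% in relative terms if 0 to 12 of 72 enrolled subjects are never exposed. It would be larger if fewer than 60 of the 72 wore a sensor, and nil if all did. This rests on two assumptions: the range for unexposed subjects, and that the events are tabulated as percentages of SS. The direction does not depend on the range: with any unexposed subject, the rate moves in the device's favour.

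The absolute change is modest and the trial's pass/fail result is untouched. The change is still worth making before analysis, because safety is part of the primary purpose and the SAP already defines nearly the set that is needed.

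**What to change.** In SAP 6.3 and 6.4 and Protocol 14.6:

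1. Keep all enrolled subjects as the set for listing every AE from consent onwards and for overall procedure-related AEs. AEs in never-exposed subjects then remain visible.
2. Add a device-exposed safety set: subjects with at least one sensor insertion attempted or made, that is, FAS#1 plus failed insertions. Report device-related AE, SADE and UADE rates on it.
3. Report FST-specific procedure AEs on subjects entering FST, who are already counted in SAP 7.1 item 4.
4. Leave per-site skin percentages as they are.

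The cost is wording. Insertion time is already documented at Visit 3 (Protocol 9.2.4.1). Failed attempts are not named as a separate data item, so the team should confirm that the sensor accountability or device deficiency forms identify them. If the protocol is not amended, SAP 7.13 is the place to record the departure from Protocol 14.6. The downside is that reported device safety rates may be slightly less favourable.

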6.4 Analysis Population Set Determination Details

- (1) No Guardian Sensor inserted: Subjects obtain randomly assigned FST, but have no Guardian Sensor inserted.
- (2) No paired Guardian Sensor and YSI TM* measurement: Subjects obtain randomly assigned FST and have a Guardian Sensor inserted, but have no paired Guardian Sensor and YSI measurement.
- (3) Violation of Inclusion/Exclusion criteria: Subjects do not meet the inclusion criteria or meet the exclusion criteria pre-specified in the protocol, and this protocol deviation may severely affect the results of primary effective endpoint. Whether protocol deviation severely affect the results of primary effective endpoints will be judged together by sponsor, investigators and statistician through discussion;
 - (4) SS= Number of subjects enrolled;

FAS#1= Number of the subjects randomly assigned FST- Number of subjects who have no Guardian Sensor inserted;

FAS^{#2}= Number of FAS^{#1} - Number of subjects who have no paired Guardian Sensor and YSI ^{TM*} measurement;

PPS= Number of FAS^{#2} - Number of subjects who have major protocol deviations (i.e. violate inclusion and exclusion criteria, etc.).

The listing of subjects who have no Guardian Sensor inserted or have major protocol deviations will be listed, including the center number, subject ID, randomly assigned FST, gender, age, type, details, FAS^{#1}, FAS^{#2} and PPS.

